8.3.2. Method of Detecting AEs and SAEs

The method of recording, evaluating, and assessing causality of AE and SAE and the procedures for completing and transmitting SAE reports are provided in Appendix [10.3](#).

Care will be taken not to introduce bias when detecting AEs and/or SAEs. Open-ended and non-leading verbal questioning of the participant is the preferred method to inquire about AE occurrences.

8.3.3. Follow-up of AEs and SAEs

After the initial AE/SAE report, the investigator is required to proactively follow each participant at subsequent visits/contacts. All SAEs will be followed until resolution, stabilization, the event is otherwise explained, or the participant is lost to follow-up (as defined in Section 7.3). Further information on follow-up procedures is provided in Appendix 10.3.

8.3.4. Regulatory Reporting Requirements for SAEs

- Prompt notification by the investigator to the sponsor of an SAE is essential so that legal obligations and ethical responsibilities towards the safety of participants and the safety of a study intervention under clinical investigation are met.
- The sponsor has a legal responsibility to notify both the local regulatory authority and other regulatory agencies about the safety of a study intervention under clinical investigation. The sponsor will comply with country-specific regulatory requirements relating to safety reporting to the regulatory authority, IRB/IEC, and investigators.
- An investigator who receives an investigator safety report describing an SAE or other specific safety information (e.g., summary or listing of SAEs) from the sponsor will review and then file it along with the IB and will notify the IRB/IEC, if appropriate according to local requirements.

8.3.5. Pregnancy

- Details of all pregnancies in female participants and, if indicated, female partners of male participants will be collected after the start of study intervention and until the follow-up visit.
- If a pregnancy is reported, the investigator should inform the sponsor within 24 hours of learning of the pregnancy and should follow the procedures outlined in Appendix 10.3.
- Abnormal pregnancy outcomes (e.g., spontaneous abortion, fetal death, stillbirth, congenital anomalies, ectopic pregnancy) are considered SAEs.
- Pregnancy (maternal or paternal exposure to investigational product) does not meet the definition of an AE. However, to fulfill regulatory requirements, any pregnancy should be reported following the SAE process described in Appendix 10.4 to collect data on the outcome for both mother and fetus.

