4.1. Overall Design

This is a Phase 1, fixed-sequence, open-label study in healthy participants that will study dabigatran P-gp DDI with selpercatinib. The anticipated study duration for each individual participant is approximately 8 weeks.

Screening

All participants will be screened within 28 days prior to enrollment (Day 1).

Treatment and Assessment Period

Eligible participants will take part in 1 treatment period. Participants will be admitted to the CRU on Day -1 and remain resident in the CRU until discharge on Day 11. All participants will receive a single dose of 150 mg dabigatran on Day 1 and a single dose of 150 mg dabigatran coadministered with a single dose of 160 mg selpercatinib on Day 8. There will be a washout period of 7 days between dosing on Days 1 and 8.

Pharmacokinetic blood sampling and safety assessments, including vital signs measurements, physical examinations, clinical laboratory tests, ECGs, and AE recording, will be performed according to the SoA (Section 1.3).

Follow-up

Participants will return to the CRU for a safety follow-up visit within 14 to 17 days after the final dose.

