5.1. Inclusion Criteria

Participants are eligible to be included in the study only if all of the following criteria apply:

Age

1. Participant must be 18 to 65 years of age, inclusive, at the time of signing the ICF.

Type of Participant

2. Participants who are overtly healthy as determined by medical evaluation including medical history, physical examination, and vital signs.
3. Participants who have clinical laboratory test results within the normal reference range for the population or investigative site, or results with acceptable deviations that are judged to be not clinically significant by the investigator.
4. Participants who have venous access sufficient to allow for blood sampling as per the protocol.

Weight

5. Have a body mass index within the range 19.0 to 35.0 kg/m² (inclusive).

Sex

6. Male or female

Contraceptive use by men or women should be consistent with local regulations regarding the methods of contraception for those participating in clinical studies.

Male participants:

- are not required to adhere to contraceptive requirements

Female participants:

- Female participants of childbearing potential (see Appendix 10.4) who are abstinent (if this is complete abstinence, as their preferred and usual lifestyle) or in a same sex relationship (as part of their preferred and usual lifestyle) must agree to either remain abstinent or stay in a same sex relationship without sexual relationships with males. Periodic abstinence (e.g., calendar, ovulation, symptothermal, post-ovulation methods), declaration of abstinence just for the duration of a study, and withdrawal are not acceptable methods of contraception.
- Female participants of childbearing potential, who are not abstinent as described above, must agree to use a highly effective method of contraception (that is, one with less than 1% failure rate) such as combination or oral contraceptives, implanted/injected contraceptives, intrauterine devices, or sterile partner until 30 days after the last dose of study medication.
 - Female participants not of childbearing potential are not required to use contraception. This includes females who are:
 - Infertile due to surgical sterilization (hysterectomy, bilateral oophorectomy, bilateral salpingectomy, or tubal ligation) or congenital anomaly (for example, Müllerian agenesis)
 - Postmenopausal as defined in Appendix 10.4.

Informed Consent

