5.2. Exclusion Criteria

Participants are excluded from the study if any of the following criteria apply:

Medical Conditions

1. Have a positive pregnancy test at screening or Day -1, where applicable
2. Are planning to become pregnant during the study or within 1 month of study completion
3. Are women who are lactating
4. Have known allergies to selpercatinib- or dabigatran-related compounds or any components of the formulation of selpercatinib or dabigatran, or history of significant atopy
5. Have a history of allergic reactions to medications or food products
6. Have a clinically significant abnormality of blood pressure and/or pulse rate as determined by the investigator
7. Have known bleeding disorder including prior personal or familiar history of abnormal bleeding, hereditary or acquired coagulation or platelet disorder, or abnormal coagulation test (prothrombin time/international normalized ratio or partial thromboplastin time/activated partial thromboplastin time greater than ULN) result at screening

8. Clinically significant abnormalities on ECG as determined by the investigator or prolongation of the QTcB or QTcF >450 msec on more than 1 ECG obtained at screening
9. Have clinically significant active cardiovascular disease or history of myocardial infarction within 6 months prior to the planned start of selpercatinib
10. Have a history or presence of cardiovascular, respiratory, renal, gastrointestinal, endocrine, hematological, or neurological disorders capable of significantly altering the absorption, metabolism, or elimination of drugs; of constituting a risk when taking the investigational product; or of interfering with the interpretation of data. Appendectomy, splenectomy, and cholecystectomy are considered as acceptable
11. Have a creatinine clearance <60 mL/min, as calculated using the CKD-EPI equation (Levey et al, 2009).

$$\text{eGFR} = 141 \times \min(S_{\text{cr}}/K, 1)^{\alpha} \times \max(S_{\text{cr}}/K, 1)^{-1.209} \times 0.993^{\text{age}}$$
$$\quad \quad \quad \times 1.018 \text{ (if female)}$$
$$\quad \quad \quad \times 1.159 \text{ (if black)}$$

12. Show a history of central nervous system conditions such as strokes, transient ischemic attacks, significant head trauma, seizures, central nervous system infections, migraine, brain surgery, or any other neurological conditions that, in the opinion of the investigator, increase the risk of participating in the study

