- Female participants of childbearing potential, who are not abstinent as described above, must agree to use a highly effective method of contraception (that is, one with less than 1% failure rate) such as combination or oral contraceptives, implanted/injected contraceptives, intrauterine devices, or sterile partner until 30 days after the last dose of study medication.
 - Female participants not of childbearing potential are not required to use contraception. This includes females who are:
 - Infertile due to surgical sterilization (hysterectomy, bilateral oophorectomy, bilateral salpingectomy, or tubal ligation) or congenital anomaly (for example, Müllerian agenesis)
 - Postmenopausal, as defined above.

Collection of Pregnancy Information

Male participants with partners who become pregnant

- The investigator will attempt to collect pregnancy information on any male participant's female partner who becomes pregnant while the male participant is in this study. This applies only to male participants who receive study intervention.
- After obtaining the necessary signed informed consent from the pregnant female partner directly, the investigator will record pregnancy information on the appropriate form and submit it to the sponsor within 24 hours of learning of the partner's pregnancy. The female partner will also be followed to determine the outcome of the pregnancy. Information on the status of the mother and child will be forwarded to the sponsor. Generally, the follow-up will be no longer than 6 to 8 weeks following the estimated delivery date. Any termination of the pregnancy will be reported including fetal status (presence or absence of anomalies) and indication for the procedure.

Female participants who become pregnant

- The investigator will collect pregnancy information on any female participant who becomes pregnant while participating in this study. The initial information will be recorded on the appropriate form and submitted to the sponsor within 24 hours of learning of a participant's pregnancy.

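### Pregnancy collection closes 14 to 17 days after the last dose, 13 to 16 days before the protocol's 30-day contraception period ends, and Section 8.3.5 and Appendix 4 conflict on pregnancies recognised after the visit

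*Protocol*

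**What the plan says.** **Collection.** Section 8.3.5 states that details of pregnancies "will be collected after the start of study intervention and until the follow-up visit". Section 4.1 places that visit: "Participants will return to the CRU for a safety follow-up visit within 14 to 17 days after the final dose". The final dose is on Day 8: "a single dose of 150 mg dabigatran coadministered with a single dose of 160 mg selpercatinib on Day 8".

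**Contraception.** Inclusion criterion 6 (Section 5.1), repeated in Appendix 4 (Section 10.4), requires women of childbearing potential who are not abstinent to use a highly effective method, ending the list of methods with "or sterile partner until 30 days after the last dose of study medication".

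**Appendix 4 on collection.** "The investigator will collect pregnancy information on any female participant who becomes pregnant while participating in this study". This limits collection by when the pregnancy begins. It gives no date after which a pregnancy that began in time can no longer be recorded.

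**After the study.** Appendix 4 requires reporting of pregnancy-related SAEs that the investigator considers reasonably related, and does not oblige the investigator to look for them. Section 8.3.1 has a similar rule for related SAEs in general. Section 8.3.5 states that pregnancy is not itself an AE.

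**The concern.** Both periods run from the last dose, yet collection stops about halfway through the contraception period, and the protocol does not explain why. Follow-up of mother and child, which Appendix 4 carries to 6 to 8 weeks past the estimated delivery date, starts only from a pregnancy that has been captured. If the wording lets one fall outside, its outcome is not obtained, although obtaining outcomes is the purpose that Section 8.3.5 gives for reporting pregnancies. These are healthy volunteers with no expected therapeutic benefit. No PK endpoint or estimate is affected; the point concerns completeness of safety capture.

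**Working it through.** The plan gives no figure for this gap, so there is none to reproduce. The inputs are final dose on Day 8, discharge on Day 11 and follow-up visit at v = 14 to 17 days after the final dose (Section 4.1); contraception to 30 days (Section 5.1, Appendix 4); selpercatinib half-life of about 32 h (Section 2.2); and up to 40 participants (Synopsis).

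**1. Days after collection closes.** Uncovered days = 30 − v; share = (30 − v)/30.
- v = 14 (study Day 22): 16 days, 16/30 = 53%.
- v = 17 (study Day 25): 13 days, 13/30 = 43%.

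Counted from the first dose, the period is 7 + 30 = 37 days and the share is 13/37 = 35% to 16/37 = 43%.

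**2. What the text captures.**

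| Pregnancy | Section 8.3.5 | Appendix 4 |
|---|---|---|
| Begins and is recognised by the visit | Collected | Collected |
| Begins before the visit, recognised after it | Collection has closed | Covered, because it began during participation |
| Begins after the visit, within 30 days of last dose | Collection has closed | Not covered, unless a related SAE comes to light |

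The second row is a conflict between the two sections. The third row is the mismatch with the contraception period.

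**3. Drug remaining**, by simple decay, 0.5^(hours/32).
- Discharge, 72 h after dosing: 72/32 = 2.25 half-lives, about 21% of selpercatinib.
- Day 14, 336 h: 336/32 = 10.5 half-lives, about 0.07%.

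Dabigatran, at 12 to 17 h (Section 2.2), has passed about 20 to 28 half-lives by day 14. Conceptions in the third row therefore follow essentially complete elimination. Those in the second row, soon after discharge, need not.

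**4. Recognition lag.** The documents give no figure. Assume that a test turns positive 10 to 14 days after conception. A test at the visit then detects conceptions only up to day 14 − 14 = 0 at the earliest and day 17 − 10 = 7 at the latest. Discharge is on day 3 after the last dose, so a conception soon after it could be missed at the visit.

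**5. Expected number.** Read the protocol's failure rate of less than 1% as annual (an assumption, since no time unit is given).
- All 40 participants in the affected group, 16 uncovered days: 40 × 0.01 × 16/365 = 0.018.
- The same 40 from discharge to day 30 (27 days): 40 × 0.01 × 27/365 = 0.030.
- With 20 such women: 0.009 and 0.015.

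**The case against.** The strongest reply is that a contraception margin may properly be longer than surveillance, and that the drug has gone by the visit. This stands for conceptions after the visit. It does not settle those that begin soon after discharge and are recognised later, where the two sections disagree.

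A second reply is that two statements in Section 8.3.5 carry no time limit: a reported pregnancy goes to the sponsor within 24 hours, and any pregnancy is to be reported through the SAE process. That stands too. A reader might infer that a late pregnancy cannot be reported at all, and the documents do not support this. What is missing is active collection, and a clear duty, for an uncomplicated pregnancy after the visit. By contrast, Section 8.3.6.1 requires sponsor notification of any reasonably drug-related product complaint learned of after discharge.

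Three further inferences also go too far:
- **That the 30 days are a declared period of risk.** The protocol states a contraception requirement and calls it nothing more.
- **That exclusion criterion 2 lengthens the period.** It excludes women who "Are planning to become pregnant during the study or within 1 month of study completion". That concerns intent at entry and sets no collection period.
- **That partners of male participants face the same mismatch.** Men "are not required to adhere to contraceptive requirements", so no contraception period is stated for them against which collection could fall short.

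**Conclusion.** The mismatch holds for non-abstinent women of childbearing potential: 13 to 16 of the 30 days (43% to 53%) fall after Section 8.3.5 closes collection, without explanation. This rests only on stated dates.

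Its practical weight is small. Fewer than about 0.03 pregnancies are expected from discharge to day 30 even if all 40 participants belonged to this group, taking the failure rate as annual. The share of days should not be read as a share of exposed pregnancies, because selpercatinib is essentially eliminated by day 14. The useful target is the conception shortly after discharge that is recognised after the visit; how many of these a test at the visit would miss depends on the assumed lag of 10 to 14 days. The change is worth making because it costs almost nothing and removes a conflict between two sections. No view is taken here on whether 30 days is the right contraception period.

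**What to change.** Reconcile Section 8.3.5 and Appendix 4 with the contraception period that the protocol already states. For female participants of childbearing potential, pregnancies should be collected and reported to the end of that period, including those that began earlier but were recognised later. At the existing follow-up visit, instruct these participants to report any such pregnancy. If the sponsor prefers the shorter period, state the reason and say how a pregnancy covered by Appendix 4 but recognised after the visit is handled.

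A telephone contact at the end of the period is optional. On the assumed lag, a call at day 30 would find only conceptions up to about day 16 to 20 (30 − 14 to 30 − 10), so the wording and the instruction do more than the call.

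Cost: a wording change in two sections and one instruction at a visit already scheduled. The reporting period for this subset runs about two weeks longer (13 to 16 days).

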8.3.6. Product Complaints

A product complaint is any written, electronic, or oral communication that alleges deficiencies related to the identity, quality, durability, reliability, safety, effectiveness, or performance of a study intervention.

The sponsor collects product complaints on investigational products and drug delivery systems used in clinical studies in order to ensure the safety of study participants, monitor quality, and to facilitate process and product improvements.

Participants will be instructed to contact the investigator as soon as possible if he or she has a complaint or problem with the investigational product so that the situation can be assessed.

NOTE: AEs/SAEs that are associated with a product complaint will also follow the processes outlined in Section [8.3.3](#) and Appendix [10.3](#) of the protocol.

8.3.6.1. Time Period for Detecting Product Complaints

- Product complaints that result in an AE will be detected, documented, and reported to the sponsor during all periods of the study in which the drug is used.
- If the investigator learns of any product complaint at any time after a participant has been discharged from the study, and such incident is considered reasonably related to a drug provided for the study, the investigator will promptly notify the sponsor.

8.3.6.2. Prompt Reporting of Product Complaints to Sponsor

- Product complaints will be reported to the sponsor within 24 hours after the investigator becomes aware of the complaint.
- The Product Complaint Form will be sent to the sponsor by email. If email is unavailable, then fax should be utilized.

8.3.6.3. Follow-up of Product Complaints

- Follow-up applies to all participants, including those who discontinue study intervention.
- The investigator is responsible for ensuring that follow-up includes any supplemental investigations as indicated to elucidate the nature and/or causality of the product complaint.
- New or updated information will be recorded on the originally completed form with all changes signed and dated by the investigator and submitted to the sponsor.

8.3.6.4. Regulatory Reporting Requirements for Product Complaints

- As required by local regulations, the investigator will report to their IRB/IEC any unanticipated adverse device effect or unanticipated problem that resulted in an SAE, or any product complaint that could have led to an SAE had precautions not been taken.

8.4. Treatment of Overdose

For the purposes of this study, an overdose of selpercatinib or dabigatran etexilate is considered as any dose higher than the dose assigned. There is no specific antidote for selpercatinib.

The antidote to dabigatran is idarucizumab and may be used in case of overdose.

In the event of an overdose, the investigator/treating physician should:

1. Contact the medical monitor immediately.
2. Closely monitor the participant for any AE/SAE and laboratory abnormalities until study intervention can no longer be detected systemically (at least 5 days).
3. Document the quantity of the excess dose as well as the duration of the overdose in the eCRF.
4. In the case of emergency uncontrolled bleeding as a direct consequence of dabigatran, urgent referral for treatment with idarucizumab should be considered.

Decisions regarding dose interruptions will be made by the investigator in consultation with the medical monitor based on the clinical evaluation of the participant.

8.5. Pharmacokinetics

- At the times and visits specified in the SoA, venous blood samples of approximately 2 mL each will be collected to determine the plasma concentrations of selpercatinib and dabigatran.
- A maximum of 3 samples may be collected at additional time points during the study if warranted and agreed upon between the investigator and the sponsor.
- Instructions for the collection and handling of biological samples will be provided by the sponsor. The actual date and time (24-hour clock time) of each sample will be recorded.

8.5.1. Bioanalysis

Samples will be analyzed at a laboratory approved by the sponsor and stored at a facility designated by the sponsor.

Concentrations of selpercatinib and dabigatran will be assayed using a validated liquid chromatography with tandem mass spectrometry method.

Bioanalytical samples collected to measure investigational product concentrations will be retained for a maximum of 1 year following last participant visit for the study.

8.6. Pharmacodynamics

Pharmacodynamic parameters are not evaluated in this study.

8.7. Genetics

A blood OR saliva sample for DNA isolation will be collected from participants.

See Appendix 10.5 for information regarding genetic research and Appendix 10.1 for details about sample retention and custody.

8.8. Biomarkers

Biomarkers are not evaluated in this study.

8.9. Immunogenicity Assessments

Not applicable for this study.

8.10. Health Economics

This section is not applicable for this study.

9. Statistical Considerations

9.1. Statistical Hypotheses

The primary objective variables will be evaluated to assess the potential drug-drug interaction. All tests and/or estimation statistics will not be confirmatory but will contribute to a body of evidence to support final conclusions.

9.2. Sample Size Determination

Approximately [REDACTED] CCI will be enrolled so that approximately [REDACTED] CCI complete the study. To evaluate the effect of selpercatinib on P-gp activity, it is important that the ratio of geometric means is estimated with reasonable precision. [REDACTED] CCI

[REDACTED]

[REDACTED]

